11. PROCEDURES INVOLVED*

See #8 above

Surgeon offices will be randomized to Usual Care or Intervention sites. During Aim 2, after completing the surveys in the clinic, usual care patients and surgeons will have the ability to

INVESTIGATOR STUDY PLAN

12.14.2021

see PRO scores, but will NOT receive feedback (no OA Care Plan) as PROs are the current standard of care in orthopedic clinics. For intervention sites, the patient and surgeon will receive the OA Care Plan (now called A.S.K. report). In Aim 3 (see details above), all patients (both study arms) will receive the A.S.K. report. In addition, patients at intervention sites will be invited to attend the ASK Coaching session to review the content of the report, discuss how to use the report in communication with the medical team, and to learn more about arthritis self-care.

Data collected include the following: New Patient Baseline [Knee/Hip] surveys; 1-month Decisional Conflict Scale;), 6-month and 12-month [Knee/Hip] surveys attached). These data collection sheets will be submitted to the IRB once they are developed.

12. DATA AND SPECIMEN BANKING*

No specimens will be banked for future use. See #13, Data Management, for data retention and access.

13. Data Analysis and Management*

Responsibility for 6 month and 12 month outcome data collection was transferred from UMMS to Northwestern during 2021. At the completion of study enrollment (on or about March 1, 2022), the UMMS data enrollment and collection services will be completed. At that date, the UMMS data center will have already, or will then, transfer all enrollment, patient-reported, and study data to Northwestern for the analytic team to manage and analyze. The UMMS data center will confirm that they expunged all ASK study data from the web-based data capture systems (DatStat, RedCap) and UMMS data storage files within UMMS.

Aim 1

We will transcribe recorded interviews and code using content analysis techniques to identify themes. We expect to achieve data saturation at or before completing 30 interviews with patients and 30 with caregivers.

AIM 2 and 3. Sample size and effect size estimates:

The trial is designed with $\geq 80\%$ statistical power at 5% significance level to detect intervention effects that are meaningful to both patients and surgeons, and health systems. In total, 40 (Aim 2) or 54 (Aim 3) surgeons will be randomized equally to treatment and control arms with an average of 100 patients/surgeon. Based on data from FORCE-TJR, the intraclass correlation within surgeon is approximately 0.02. Using two independent group t-tests adjusting for within surgeon clustering, the trial can detect an intervention effect of (a) improved decision quality of >0.16 SD ; (b) improved quality of OA care defined in two ways: 6 month post-decision pain relief (KOOS/HOOS) of ≥ 3.3 points for TKR patients (34.1 vs. 37.4; SD=20.8) and ≥ 3.3 for THR patients (45.7 vs. 49.0; SD=20.9) or greater proportion of patients with meaningful pain relief (17 points in HOOS/KOOS pain score) of $\geq 6.1\%$ more TKR patients (77.9% vs. 84.0%) and $\geq 4.2\%$ more THR patients (90% vs. 94.2%).

Aims 2 and 3: Overview of analytic approach. We hypothesize (Aim 2) that patient/clinician use of the OA Careplan will improve decision quality as well as

INVESTIGATOR STUDY PLAN

12.14.2021

satisfaction with the OA care decision, as compared to usual care. Further, we hypothesize that improved decision quality will mediate quality of OA care as measured by lower pain and higher function at 6 and 12 months (KOOS/HOOS) after decision for both TJR and non-operative care. In Aim 3, we hypothesize that the OA Careplan+Support (vs. OA Careplan alone) will incrementally enhance decision quality and quality of OA care (for those who choose to use the Support) with the same measures used in Aim 2.

The general analytic approaches for Aims 2 and 3 are similar and summarized here. The underlying models extend our previous award-winning TKR outcome prediction model where discrete outcome sub-groups were identified. We will adhere to the intent-to-treat principle to analyze the trial data; the intervention status of the surgeon/site and their patients will be analyzed according to their status at the time of intervention. First, descriptive statistics for all relevant outcomes will be tabulated by treatment arm. Select patient factors (e.g., race, sex, function; comorbid factors) that may contribute to heterogeneity of treatment effects will be compared using univariate methods such as t-test for normally distributed variables, Wilcoxon rank sum test for skewed continuous variables, or Chi² test for categorical variables. We will examine distributions of outcomes, identify proper distribution assumptions, and determine whether or what types of transformations are indicated.

Because the trial data are hierarchical in nature (repeated measures of the same patient nested within participating surgeons/sites), we will use hierarchical generalized linear latent and mixed models (GLLAMM) to analyze the trial data. The model will consider information at the patient and surgeon levels. The basic unit of analysis is at the patient level. Patients nested within the surgeon/site will be considered exchangeable, and sites/surgeons are considered independent from each other. To account for potential imbalance in site/surgeon and patient characteristics, we will adjust for surgeon/site and patient factors in the regression models. Candidate patient level covariates include joint pain severity, pre-decision physical function level, and comorbid conditions, such as diabetes, renal disease, pulmonary disease, depression, obesity, or congestive health failure. Candidate surgeon variables for adjustment include annual surgical volume, procedure type, or geographic region of US. We will follow the parsimonious principle to derive the final models for evaluating intervention effects. First, we will use GLLAMM models to analyze the association of each plausible patient-and site/surgeon-level factor with the outcomes (quality of decision, change in pain severity, function). Those statistically significant variables ($p < 0.10$) will be included in a subsequent analysis using multivariable models to identify a parsimonious set of independent patient-and site/surgeon-level covariates. Model development will be guided by clinicians and patient advisors to assure that clinically important variables are included. To identify independent site/surgeon-level variables, we will include each of the significant variables separately while forcing the patient-level covariates into the models. The significance of each site/surgeon-level variable will be determined using (partial) likelihood ratio tests. We will identify a subset of site/surgeon indicators that contribute to outcomes ($p < 0.10$), independent of individual-level factors. Furthermore, this subset of significant indicators

INVESTIGATOR STUDY PLAN

12.14.2021

will be entered into the same model in order to assess their contributions to the outcome under analysis, after adjusting for each other, as well as the patient-level covariates. Model assumptions will be carefully examined. In these model-building processes, effect modifications will be examined by including interaction terms between relevant covariates, and to ensure the heterogeneity of the intervention effects among patient subgroups are adequately considered. The analyses will be conducted with all patients; and then for TKR and THR patients separately. While the primary goal is to understand patient-level covariates with outcomes, it is critical to assess surgeon/site factors that may influence outcome for all, or sub-groups of patients. For example, obese, diabetic patients with cardiac disease may have more positive decision quality and pain relief with a more experienced high-volume surgeon.

Aim 2: To assess the effect of OA Careplan on (a) decision quality and (b) pre-to- post decision pain relief and functional gain, we will do the following. We expect 20 surgeons and 2000 patients will receive the OA Careplan intervention, and another 20 surgeons and 2000 patients will receive usual care. The analyses will be conducted with all patients; and then for TKR and THR patients separately. First, we will tabulate the decision quality and care outcomes by arm and for select patient subgroups (e.g., sex, age, race/ethnicity). Second, we will use GLLAMM to estimate adjusted Careplan intervention effects by including in the models a Careplan indicator (Careplan intervention=1 vs. usual care=0) and a set of site/surgeon and patient variables for adjustment. A statistically significant coefficient of the Careplan indicator signals possible intervention effect. In this analysis, interaction terms between the Careplan indicator and surgeon or patient factors will be examined, statistically significant interaction terms may suggest the existence of heterogeneity in intervention effects. If present, intervention effects will be analyzed and presented by subgroups.

Aim 3: To evaluate the effect of the OA Careplan+Support (Coaching) on (a) decision quality and (b) pre-to-post decision pain relief and functional gain, we will do the following. The 20 surgeons (and their patients) who received usual care in Aim 2 will receive the OA Careplan intervention (n=2,000) in Aim 3. The 20 surgeons who received the OA Careplan in Aim 2 will now receive the OA Careplan+Support (n=2,000 new patients) in Aim 3. Additional surgeons will be recruited and randomized to the 2 arms. First, we will compare patient characteristics between users and non-users of the SUPPORT. We will then identify patient as well as site/surgeon determinants of the use of the SUPPORT using multi-level logistic regression models, and estimate individual patient's probability (propensity) for any use of SUPPORT strategies. Because use of the SUPPORT is not randomized, we will use inverse propensity weighting approach to estimate the effects of the SUPPORT on outcomes (decision quality, pain, function).

We will begin with descriptive analysis, and estimation of crude OA Careplan+Support intervention effects, overall and by select patient subgroups. We will further use GLLAMM to estimate covariate---adjusted intervention effects, overall and by patient

INVESTIGATOR STUDY PLAN

12.14.2021

subgroup, and adjust for propensity scores, plausible surgeon and patient factors. Statistically significant differences between the two arms indicate possible incremental SUPPORT intervention effect beyond the OA Careplan alone. We will conduct pre-post comparisons of the outcomes (decision quality, pain relief) for patients of the 20 surgeons who were in the OA Careplan intervention arm in Aim 2 and are now in the OA Careplan+Support arm.

Statistically significant pre-post changes in outcomes support possible incremental effects of the SUPPORT intervention. We will derive a usage score of the SUPPORT system (e.g., frequency and duration of use) as an indicator of “dosage” of use and use it to estimate a possible “dose-response” relationship between level of use and patient outcomes in the GLLAMM. We will also identify relevant patient-and site/surgeon predictors of any and higher levels of usage.

Second, we will use GLLAMM to analyze the differences in joint pain and function at 6 and 12 months after the care decision between OA Careplan and comparison arms. We will pool data from both arms in the two phases. We will include an indicator variable to represent intervention status (usual care, OA Careplan, or OA Careplan+Support). We will assess whether 6 and 12 month pain differ between intervention arms. Next, we will repeat this process for the patients with meaningful (>17 point) change in HOOS/KOOS pain score. We expect pain relief will be significantly improved in the OA Careplan arm, with greater improvement to occur in the OA Careplan+Support, compared to the usual care group. Finally, we will formally test the mediation effects of Careplan and Careplan+Support on pain relief and functions at 6 and 12 months, using the two level structural equation models with mediation effects by Krull and MacKinnon (2001) and Preacher, Zyphur and Zhang (2010).

Only those listed in our IRB application will have access to identified data.

At this time, there is no plan to destroy the Patient Reported Outcome (PROs) data because of the value to this data regarding national norms for PROs for patients electing to have surgery and those electing non-surgical management of OA.

PHI including individual contact information for follow-up date collection will be destroyed after all surveys have been completed by individual patients 3 years after the completion of the study.

Published data derived from this study will consist of statistical analyses collapsed (averaged) across participants. Under no circumstances will data from individual participants be identifiable in reports or published manuscripts.

INVESTIGATOR STUDY PLAN

12.14.2021

Qualitative Interviews of Patients, Analyses: We will transcribe recorded interviews and check transcripts for accuracy. We will code transcripts using content analysis techniques to identify themes. All identifiers will be removed from transcripts before they are uploaded to a web-based qualitative analysis program Dedoose (<http://www.dedoose.com/>). Two members of the research team will review an initial subset of transcripts and independently generate an initial code book. The code list will be discussed with the research team prior to finalizing. An additional subset of transcripts will be coded using the code book by a pair of coders who will compare their results periodically to reconcile their independent applications of codes. All transcripts will then be coded, and the research team will organize the codes into content areas to summarize findings. Personal identifiable data from individual participants will not be included in reports or published manuscripts.

Qualitative Interviews of Surgeons, Analyses: Interviews will be qualitatively analyzed. Transcripts will be checked for accuracy before being uploaded into the web-based qualitative analysis program Dedoose (<http://www.dedoose.com/>). All identifiers will be removed from transcripts before they are uploaded. Two members of the research team will begin by reviewing transcripts as they are uploaded to Dedoose and independently generating an initial code list. The code list will be discussed with the research team prior to finalizing. Pairs of coders will apply codes to transcripts and compare their results periodically to reconcile their independent applications of codes. In cases where coder pairs are not able to reconcile code applications, the codes will be presented to the research team during weekly study meetings to examine and adjudicate codes together. Individual coders will be free to propose new codes they feel are not adequately represented on the operational coding list. These proposals will be made at weekly study meetings and accepted codes will be applied to the dataset by coder pairs accordingly. Once coding is complete, the research team will organize the codes into content areas to summarize findings.

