4. OBJECTIVES*

We propose to prospectively randomize orthopedists, with their patients, to receive (or not) a real-time, web-based system intervention: the OA Care plan. The OA Care plan will include individualized, patient-centric information: (1) trended patient-reported OA pain and function, (2) tailored estimates of likely TJR benefits and risks based on a contemporary US cohort of 25,000 TJR patients (FORCE-TJR Registry), (3) evidence-based information for non-operative care, and (4) individual patient goals.

Specific Aims include:

Aim 1. Patients and their Caregivers/Trusted Others will refine the design, content, and usability of a real-time, web-based individual OA Care plan to guide TJR and non-operative OA care decisions.

Aim 2. Randomize 40 orthopedists, and their patients, to receive the OA Care plan at the time of orthopedic consultation (intervention) vs. usual care (control) and compare (a) OA care decision process and quality and (b) quality of OA care as measured by pain relief and functional gain in the two arms at 6 and 12 months after the decision, and assess the impact of decision quality on quality of OA care.

Aim 3. Randomize 36-40 orthopedists, and their patients, to receive the OA Care plan plus peer, family, and primary care physician support (OA Care plan+Support; intervention called A.S.K. Coaching) vs. the OA Care plan alone and compare the quality of OA care decision and quality of care (pain relief, functional gain) in the two arms.

When moving the PCORI contract to Northwestern in early 2019, we revised the sample size estimates required to meet the same study power and analytic plan for both Aim 2 and Aim 3. Using the early study data, we determined that n=3000 patients in Aim 2 and n=3000 patients in Aim 3 was adequate to meet statistical goals. We also determined that fewer surgeons (N= 36-40) would be required in Aim 3 to consent 3000 patients. PCORI agreed to the changes in number of surgeons and patients. We clarified this change in the ISP.

Based on the components of the Chronic Care Model, this technology-delivered, individualized OA Care plan will enable patients and clinicians to make treatment decisions based on patient symptoms, goals, and comparative effectiveness evidence. We hypothesize that OA Care plan users, as compared to usual care, will report greater decision quality for both TJR or non-

INVESTIGATOR STUDY PLAN

12.14.2021

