7. STUDY-WIDE NUMBER OF SUBJECTS*

Aim 1 Patient Interviews= 30 participants

Caregiver/Trusted Other Interviews = 30 participants

Aims 2 and 3 6000 patients total, 3000 in Aim 2 and 3000 in Aim 3

20-30 surgeon offices will have 1-2 surgeons for each office (total 40 surgeons) contribute 100 consecutive new patients to the study for Aim 2 and an additional 100 patients for Aim 3.

For surgeon qualitative interviews: up to 35 MD surgeons. MD surgeons are not subjects in the ASK study (patients are).

For Aim 3 patient qualitative interviews: Up to 50 patients, with an approximately even breakdown from each of the following groups

- Participated in A.S.K. Coaching + self-reported (on 1-month survey) surgery planned and use of OA Care plan with MD.
- Participated in A.S.K. Coaching + self-reported (on 1-month survey) non-surgical treatment planned and use of OA Care plan with MD.
- Participated in A.S.K. Coaching + self-reported (on 1-month survey) surgery planned and no use of OA Care plan with MD.
- Participated in A.S.K. Coaching + self-reported (on 1-month survey) non-surgical treatment planned and no use of OA Care plan with MD.
- Usual Care arm + self-reported (on 1-month survey) surgery planned and use of OA Care plan with MD.
- Usual Care arm + self-reported (on 1-month survey) non-surgical treatment planned and use of OA Care plan with MD.

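### The power paragraph still describes 40 or 54 surgeons at 100 patients each; on its own ICC, the current 3,000 patients per aim give slightly under 80% power in both aims

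*Combined protocol and SAP*

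**What the plan says.** Section 13 (sample size and effect size estimates) claims at least 80% power at the 5% level and states: "In total, 40 (Aim 2) or 54 (Aim 3) surgeons will be randomized equally to treatment and control arms", "with an average of 100 patients/surgeon". It adds that "the intraclass correlation within surgeon is approximately 0.02". One set of detectable effects is given for both aims: 0.16 SD for decision quality; 3.3 points of pain relief (SD 20.8 knee, 20.9 hip); and responder rates of 77.9% vs 84.0% (knee) and 90% vs 94.2% (hip).

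Other sections give different numbers:

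- Section 4 sets 3,000 patients in each aim, 40 surgeons in Aim 2 and 36-40 in Aim 3: "We also determined that fewer surgeons (N= 36-40) would be required in Aim 3 to consent 3000 patients". It says the sample size was revised from early data so as to keep the power unchanged.
- Section 7 gives 3,000 patients per aim, but also "total 40 surgeons) contribute 100 consecutive new patients to the study for Aim 2 and an additional 100 patients for Aim 3", which makes 40 x 100 = 4,000 per aim.
- Section 13, Aim 2 paragraph, expects 20 surgeons and 2,000 patients in each arm, again 4,000.
- Section 13, Aim 3 paragraph, carries over those 40 surgeons with 2,000 patients per arm and then says: "Additional surgeons will be recruited and randomized to the 2 arms". That makes more than 40.

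**The concern.** Section 4 reports that the design was changed, but the power paragraph was not changed with it. That paragraph now describes neither aim's current size, and the text contains several different Aim 3 designs. In a trial randomised by surgeon, both the number of surgeons and the number of patients per surgeon determine power, so a reader cannot tell which design the claim of at least 80% belongs to.

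This matters most if a result is null. Each aim would then be read against a stated power and detectable effect calculated for a different number of patients, and in Aim 3 possibly of surgeons. Aim 3 looks for an increment over an arm that already receives the Careplan, so a null result there is quite possible.

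**Working it through.** **Inputs.** From section 13: ICC 0.02; 5% level; power of at least 80%; t-test adjusted for clustering; effects 0.16 SD and 3.3 points with SD 20.8 (3.3/20.8 = 0.159 SD). From section 4: 3,000 patients per aim; 40 surgeons (Aim 2), 36-40 (Aim 3). Assumed, because not stated: two-sided test, equal cluster sizes, no attrition.

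**Formulas.** With S surgeons in total and m patients each:

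- design effect DE = 1 + (m - 1) x 0.02
- effective n per arm = (S/2) x m / DE
- standard error in SD units = sqrt(2 / effective n)
- power from the noncentral t with S - 2 degrees of freedom (t), or the normal approximation (z)
- detectable effect at 80% power = (critical value + 80% quantile) x standard error

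**Reproducing the plan's figure.** 40 surgeons x 100: DE = 1 + 99 x 0.02 = 2.98; effective n = 20 x 100 / 2.98 = 671 per arm; standard error = sqrt(2/671) = 0.0546. The detectable effect is 0.157 SD (t) or 0.153 SD (z), which is 3.27 or 3.18 points. Power at 3.3 points is 80.8% / 82.8%, and the two responder contrasts give 81.3% and 81.5%. This fits the stated 0.16 SD and 3.3 points.

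54 surgeons x 100: effective n = 27 x 100 / 2.98 = 906 per arm; detectable effect 0.134 / 0.132 SD (2.79 / 2.74 points). The quoted effects are therefore the 40-surgeon figures, not a 54-surgeon calculation.

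**Current design.** 40 surgeons, 3,000 patients: m = 75; DE = 1 + 74 x 0.02 = 2.48; effective n = 20 x 75 / 2.48 = 605. 36 surgeons, 3,000 patients: m = 83.3; DE = 2.647; effective n = 18 x 83.3 / 2.647 = 567.

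| Surgeons x patients | Total | Power at 0.16 SD (t / z) | Power at 3.3 points (t / z) | Detectable effect, SD (t / z) | Points (t / z) |
|---|---|---|---|---|---|
| 54 x 100 | 5,400 | 91.7% / 92.6% | 91.2% / 92.2% | 0.134 / 0.132 | 2.79 / 2.74 |
| 40 x 100 | 4,000 | 81.5% / 83.4% | 80.8% / 82.8% | 0.157 / 0.153 | 3.27 / 3.18 |
| 36 x 100 | 3,600 | 77.1% / 79.4% | 76.4% / 78.7% | 0.166 / 0.161 | 3.45 / 3.35 |
| 54 x 55.6 | 3,000 | 84.5% / 85.8% | 83.9% / 85.2% | 0.151 / 0.148 | 3.14 / 3.08 |
| 40 x 75 (Aims 2 and 3) | 3,000 | 77.4% / 79.5% | 76.7% / 78.8% | 0.165 / 0.161 | 3.44 / 3.35 |
| 36 x 83.3 (Aim 3) | 3,000 | 74.4% / 76.8% | 73.7% / 76.1% | 0.171 / 0.166 | 3.56 / 3.46 |

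**Which change crosses 80%?** Going from 54 to 40 surgeons at 100 patients each leaves power above 80%. So does 3,000 patients spread over 54 surgeons, a design that no section describes. At 40 surgeons it takes the further cut from 100 to 75 patients each. At 36 surgeons the count alone is enough, and the cut to 83 patients each widens the gap. In Aim 2 the surgeon number is unchanged, so the whole gap comes from patients per surgeon.

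**ICC that would restore 80% at 0.16 SD with 3,000 patients.** 40 surgeons: 0.0179 (t) or 0.0195 (z). 36 surgeons: 0.0159 (t) or 0.0176 (z).

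**The case against.** The strongest reply is that section 4 already deals with power. It says the revised numbers were derived from early data to keep power the same and were found adequate. If the early data gave an ICC of roughly 0.016 to 0.0195, power of 80% at 0.16 SD is restored, and a value in that range would still round to the stated 0.02. The planned models also adjust for baseline pain and function, which an unadjusted t-test calculation ignores. And the gap is small: at 40 surgeons it is half a point by the normal approximation and 2.6 points by the t method.

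Much of this stands. It rules out saying that the trial lacks 80% power; it permits saying only that the inputs shown do not give 80%. It does not rescue the text, because section 4 reports no revised ICC, SD or cluster size, and section 13 still gives 0.02. The gain from covariate adjustment is not quantified either. In the other direction, the power paragraph makes no allowance for non-response: if 10-30% is assumed, power at 3.3 points falls to about 70-77% with 40 surgeons and 67-75% with 36.

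A reader might also infer from the 54 versus 36-40 discrepancy that the loss of surgeons is what undermines Aim 3, and that Aim 2 is unaffected. The figures do not support this. The stated effects hold at 40 surgeons x 100, and Aim 2 at 40 x 75 has the same gap as Aim 3 at 40 x 75.

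**Conclusion.** The power paragraph is out of date and inconsistent with sections 4 and 7, and the rest of section 13 is not aligned either. On the plan's stated ICC, the current design falls short of the claimed 80% by about 0.5 to 6 percentage points. The detectable effect at 80% power rises to 0.161-0.165 SD with 40 surgeons and up to 0.171 SD with 36, or 3.35-3.56 points. The lower end applies to both aims; the upper end applies to Aim 3 with 36 surgeons.

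This rests on a two-sided 5% test, equal clusters, no attrition, ICC 0.02 and, as the plan's own 3.3-point figures require, all patients counting towards each joint's contrast. The inconsistency in the numbers needs none of these assumptions. The stronger conclusion, that the promised power is not delivered, goes further than the documents allow, because the early-data re-estimate is reported without its inputs. The point is worth correcting but does not threaten the design.

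**What to change.** In section 13, replace 54 surgeons and 100 patients per surgeon with the current numbers for both aims: 3,000 patients each, 40 surgeons in Aim 2 (75 per surgeon) and 36-40 in Aim 3 (about 75-83 per surgeon). Make section 7 and the Aim 2 and Aim 3 analysis paragraphs of section 13 agree, including the 2,000 per arm and the additional surgeons. Then do one of two things:

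- keep ICC 0.02 and restate either the detectable effects (about 0.161-0.165 SD for 40 surgeons, up to 0.171 SD for 36; 3.35-3.56 points) or the power at 0.16 SD (77.4-79.5% and 74.4-76.8%); or
- report the ICC, SD and cluster size from the early-data re-estimate in section 4, with the detectable effects they give.

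Either way, state the sidedness of the test and any allowance for non-response. This is a change of wording only. It needs no extra surgeons or patients; its one cost is that the stated figure may become slightly less favourable.

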If the Research Coordinator is unable to reach the potential participant by phone, the Final contact Recruitment and Follow-up-e-mail-snail mail 2-14-18 letter will be sent to the patient either by email or snail mail (see attached). This letter will also be used if consented participants do not return follow-up surveys.

Surgeon offices will be randomized to Usual Care or Intervention sites. During Aim 2, after completing the surveys in the clinic, usual care patients and surgeons will have the ability to see PRO scores, but will NOT receive feedback (no OA Care Plan). This is the current standard of care in orthopedic clinics. For intervention sites, the patient and surgeon will receive the OA Care Plan (named the A.S.K. Report).

INVESTIGATOR STUDY PLAN

12.14.2021

The DCC will follow-up with patients at 3 time points: 1-month Decisional Conflict Scale and Shared Decision Making Process Survey; 6 months and 12 months after surgery or decision to use non-surgical method of managing OA. (see 1-month Decisional Conflict Scale, 6 and 12-month [Knee/Hip] surveys attached). Surveys will be mailed and/or emailed based on participant preference. The 12 month surveys are standard clinical care; the 1 month, and 6 month contact are for the research. After receiving IRB approval (hopefully September 2020), newly enrolled patients will also respond to Covid-19 measures via the same web-based data capture system used in the rest of the study at 1-month, 6 months and 12 months.

Participants will receive a \$20 gift card after completing the 1-month Decisional Conflict Scale for their time

During Aim 3, Usual Care sites will receive the OA Care Plan (A.S.K. Report), and Intervention sites will receive the Enhanced OA Care Plan, including access to Patient Peer Support website and PCP reports. All surgeons that used the OA Care plan in Aim 2 will be invited to participate in the Enhanced OA Care plan in Aim 3.

When patients are contacted to complete the post-visit 1-month Decisional Conflict Scale, we will inquire as to whether the surgeon and patient reviewed the A.S.K. Report together. This allows us to understand report use rates for all patients.

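### Aim 2's 80% power for a 3.3-point pain difference at 6 months allows for neither unreturned surveys nor unequal surgeon volumes, and has only about 1 to 3 percentage points of slack

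*Combined protocol and SAP*

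**What the plan says.** Section 13 (sample size and effect size estimates) sets at least 80% "statistical power at 5% significance level". It gives the numbers of clusters as "In total, 40 (Aim 2) or 54 (Aim 3) surgeons will be randomized equally to treatment and control arms", "with an average of 100 patients/surgeon", and says that "the intraclass correlation within surgeon is approximately 0.02". The test is a two-group t-test adjusted for clustering by surgeon. The pain outcome is introduced as "improved quality of OA care defined in two ways: 6 month post-decision pain relief", with a detectable difference of "3.3 points for TKR patients (34.1 vs. 37.4; SD=20.8"). The hip figure is also 3.3 points, with SD 20.9, and the decision-quality figure is 0.16 SD.

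The 100 counts patients enrolled. In Section 7 the surgeons "contribute 100 consecutive new patients to the study for Aim 2". The Aim 2 analysis text in Section 13 carries 20 surgeons and 2,000 patients per arm into the analysis with nothing deducted. Section 8 says that surveys go out by mail or email, and of the final-contact letter it says: "This letter will also be used if consented participants do not return follow-up surveys".

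Section 4 reports that both aims were later revised to 3,000 patients, with 36 to 40 surgeons in Aim 3, for the same power. It shows no calculation. No section states a 6-month return rate, an allowance for loss, or a spread of patients per surgeon.

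**The concern.** Pain relief at 6 months is part of the primary outcome in Section 10. It is measured by a survey that some patients will not return, and surgeons seldom recruit at the same rate. Each of these lowers power in a cluster-randomized trial. If the stated figure already needs complete returns and equal clusters, the margin above 80% is all there is to absorb both. The 3.3-point benchmark would then be somewhat optimistic, and a null pain result might be read against a difference that the trial was less able to detect than stated.

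**Working it through.** **Inputs from the documents.** Aim 2: k = 20 surgeons per arm, m = 100 patients per surgeon, ICC = 0.02, SD = 20.8, difference 3.3, alpha 0.05. Sidedness is not stated; two-sided is assumed.

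**Inputs the documents do not give.** Loss d at 6 months (0% to 30% assumed, spread evenly over surgeons) and the coefficient of variation (CV) of surgeon size (0 to 0.7 assumed).

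**Reproducing the stated figure.**
- Design effect = 1 + (m − 1) × ICC = 1 + 99 × 0.02 = 2.98.
- Effective n per arm = 2,000 / 2.98 = 671.
- Standard error = 20.8 × √(2/671) = 1.136, so 3.3 points is 2.91 standard errors.
- Noncentral t, df = 40 − 2 = 38: power 80.8%, detectable difference 3.26 points (0.157 SD). For hips (SD 20.9), 80.5% and 3.28 points.
- Normal approximation: power 82.8%, detectable difference 3.18 points (0.153 SD).

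The t results round to the plan's own 3.3 points and 0.16 SD. The normal results round to 3.2 and 0.15. So the slack is 0.8 percentage points on the method that best matches the stated figures, and 2.8 on the other. Both use 100 analysed patients for every surgeon.

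**Adding loss and unequal size.** Replace m by 100 × (1 − d). For unequal clusters, two treatments:
- Patient-level design effect: 1 + ((1 + CV²) × m − 1) × ICC.
- Mixed-model weighting: multiply the equal-cluster effective n by 1 − CV² × L × (1 − L), with L = m × ICC / (m × ICC + 1 − ICC). This is closer to the hierarchical model that Section 13 plans.

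Example, 20% loss and CV 0.5, so m = 80. The patient-level design effect is 1 + (1.25 × 80 − 1) × 0.02 = 2.98, and effective n = 1,600 / 2.98 = 537. With mixed-model weighting, L = 1.6 / 2.58 = 0.620, relative efficiency = 1 − 0.25 × 0.620 × 0.380 = 0.941, and effective n = (1,600 / 2.58) × 0.941 = 584.

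| Aim 2, 40 surgeons × 100 enrolled | Power, t | Power, normal | Detectable, t | Detectable, normal |
|---|---|---|---|---|
| No loss, equal sizes | 80.8% | 82.8% | 3.26 | 3.18 |
| 10% loss | 79.4% | 81.5% | 3.32 | 3.24 |
| 20% loss | 77.7% | 79.8% | 3.40 | 3.31 |
| 30% loss | 75.5% | 77.7% | 3.49 | 3.40 |
| CV 0.5, mixed-model weighting | 78.6% | 80.7% | 3.36 | 3.27 |
| CV 0.5, patient-level design effect | 74.6% | 76.7% | 3.53 | 3.44 |
| 20% loss and CV 0.5, mixed-model weighting | 75.2% | 77.4% | 3.50 | 3.41 |
| 20% loss and CV 0.5, patient-level design effect | 71.7% | 73.9% | 3.65 | 3.56 |

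From loss alone, power drops below 80% once loss exceeds 6.3% (t) or 18.8% (normal).

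**At the current numbers, with no loss and equal sizes.**
- Aim 2: 3,000 / 40 = 75 per surgeon. Design effect 1 + 74 × 0.02 = 2.48; effective n = 1,500 / 2.48 = 605. Power 76.7% (t) or 78.8% (normal); detectable difference 3.44 or 3.35 points.
- Aim 3 at 36 surgeons: 3,000 / 36 = 83.3 per surgeon. Design effect 2.65; effective n = 567. Power 73.7% (t, df 34) or 76.1% (normal).
- Aim 3 at the 54 surgeons × 100 of Section 13: effective n = 2,700 / 2.98 = 906. Power 91.2% (t, df 52), and still 84.2% with 20% loss and CV 0.5 on the less favourable design effect.

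**The case against.** The best defence is that nothing was miscalculated: 3.3 points and 0.16 SD both reproduce. That is right, and the point is an omitted allowance, not an arithmetic error.

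A reader might infer that the stated effect is simply not delivered. At 40 × 100 the documents do not support that, because every shortfall there depends on a return rate or CV that they do not give. With 10% loss alone the detectable difference is 3.32 by t, which still rounds to 3.3, and the normal approximation keeps power above 80%. Section 13 does not state its degrees of freedom, and its ICC is only approximate: at 0.018, power would be 83.4% (t).

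Nor do the documents say that clusters are equal in size. That is inferred from what the calculation needs. Section 7 sets a target of 100 per surgeon, which would limit the spread if it were met, and nothing supports a particular CV. The planned mixed model also softens the penalty for unequal size, so the patient-level design effect is the pessimistic end.

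Section 13 lists baseline pain and function as candidate covariates, while the power calculation is unadjusted. A reduction in total variance of about 1.4% would restore 80% (t) at 10% loss; about 6% would do so at 20% loss; and about 11% at 20% loss with CV 0.5 under mixed-model weighting. These reductions are as much assumptions as the losses, but they are plausible offsets.

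It can also be said that 40 × 100 has been superseded. That does not rescue the claim: on the stated ICC and SD, the smaller current numbers start below 80%. Section 4 says that the revision drew on early study data, so its inputs may have changed, but it shows none.

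**Conclusion.** The point holds in a limited, conditional form. For Aim 2, the claim of at least 80% power for 3.3 points at 6 months treats enrolled patients as complete cases and surgeons as equal in size. Its slack is about 1 percentage point (t) to 3 (normal), while the plan itself foresees unreturned surveys. If loss is 20% and CV 0.5, both assumed, power is about 72% to 77% and the detectable difference about 3.4 to 3.65 points. That is a moderate shift.

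It would be wrong to extend this to Aim 3 at 54 surgeons, where power stays above 80% in the same scenario. At the numbers in Section 4 no assumed loss is needed: Aim 2 is at 76.7% to 78.8%, and Aim 3 with 36 surgeons at about 74% to 76%. Those figures rest on ICC 0.02, SD 20.8, equal sizes and no covariate adjustment.

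**What to change.** In Section 13, restate the detectable 6- and 12-month pain differences, or the power for 3.3 points, separately for each aim at the current numbers of surgeons and patients.

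- Use returned surveys per surgeon, taken from the observed Aim 2 return rate at each time point.
- Use the observed variation in patients per surgeon. Section 8 says that enrolment records are kept by site.
- Use a design effect or relative efficiency that matches the planned mixed model, and state the test, sidedness and degrees of freedom. If credit is taken for baseline adjustment, state the variance reduction assumed.
- Report these figures apart from the 1-month decision outcome. In Aim 3 that assessment is completed before the coaching invitation, following verbal consent, so its losses may be quite different.

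The cost is a short recalculation and a slightly less favourable stated figure. No extra patients are needed.
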